6.2.3 Number of Study Devices to Be Used

Each subject will receive one study stent.

6.3 Subjects

The trial population will consist of approximately 50 male and female subjects undergoing PCI for angina (stable or unstable), silent ischemia (in absence of symptoms a visually estimated target lesion diameter stenosis of $\geq 70\%$, a positive non-invasive stress test, or FFR ≤ 0.80 must be present), non ST elevation MI (NSTEMI), or recent ST elevation MI (STEMI >24 hours prior to enrollment and stable).

Complex lesions are allowed (enrolled after successful pre-dilatation or aspiration thrombectomy). There is no limit to the number of lesions per vessel or individual lesion length.

Subjects must sign an EC approved Subject Informed Consent Form, and meet all the general and angiographic eligibility criteria before being enrolled to the trial.

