6.3.1 Inclusion Criteria for Subject Selection

All inclusion criteria must be present for the patient to be eligible for enrollment.

Note: the I/E criteria refer to the patient's baseline condition prior to PCI.

General Inclusion Criteria

1. Age ≥ 18 years.
2. Patient with an indication for PCI including angina (stable or unstable), silent ischemia (in absence of symptoms a visually estimated target lesion diameter stenosis of $\geq 70\%$, a positive non-invasive stress test, or FFR ≤ 0.80 must be present), NSTEMI, or recent STEMI. For STEMI the time of presentation to the first treating hospital, whether a transfer facility or the study hospital, must be >24 hours prior to enrollment and enzyme levels (CK-MB or Troponin) demonstrating that either or both enzyme levels have peaked.
3. An attempt (whether successful or not) was made to implant a 38 mm EluNIR stent (Stent was advanced beyond the guiding catheter).

4. Non-target vessel PCI are allowed prior to enrollment depending on the time interval as follows:

a. During Baseline Procedure:

PCI of non-target vessels performed during the baseline procedure itself immediately prior to enrollment if successful and uncomplicated defined as: <50% visually estimated residual diameter stenosis, TIMI Grade 3 flow, no dissection \geq NHLBI type C, no perforation, no persistent ST segment changes, no prolonged chest pain, no TIMI major or BARC type 3 bleeding.

b. Less than 24 hours prior to Baseline Procedure:

Not allowed (see exclusion criteria #2).

c. 24 hours-30 days prior to Baseline Procedure:

- i. PCI of non-target vessels 24 hours to 30 days prior to enrollment if successful and uncomplicated as defined above.
- ii. In addition, in cases where non-target lesion PCI has occurred 24-72 hours prior to the baseline procedure, at least 2 sets of cardiac biomarkers must be drawn at least 6 and 12 hours after the non-target vessel PCI.
- iii. If cardiac biomarkers are initially elevated above the local laboratory upper limit of normal, serial measurements must demonstrate that the biomarkers are falling.

d. Over 30 days prior to Baseline Procedure:

PCI of non-target vessels performed greater than 30 days prior to procedure whether or not successful and uncomplicated.

5. Patient or legal guardian is willing and able to provide informed written consent and comply with follow-up visits and testing schedule.

Angiographic inclusion criteria (visual estimate)

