6.3.2 Exclusion Criteria for Subject Selection

All exclusion criteria must be absent for the patient to be eligible for enrollment.

General Exclusion Criteria

1. STEMI within 24 hours of initial time of presentation to the first treating hospital, whether at a transfer facility or the study hospital or patients in whom enzyme levels (either CK-MB or Troponin) have not peaked.

2. PCI within the 24 hours preceding the baseline procedure.
3. Non-target lesion PCI in the target vessel within 12 months of the baseline procedure.
4. History of stent thrombosis.
5. Cardiogenic shock (defined as persistent hypotension (systolic blood pressure <90 mm/Hg for more than 30 minutes) or requiring pressors or hemodynamic support, including IABP).
6. Subject is intubated.
7. Known LVEF <30%.
8. Relative or absolute contraindication to DAPT for 6 months in non-ACS patients and 12 months in ACS patients (including planned surgeries that cannot be delayed, or on or indicated for chronic oral anticoagulant treatment).
9. eGFR<30 ml/min/1.72 m²
10. Hemoglobin <10 g/dL.
11. Platelet count <100,000 cells/mm³ or >700,000 cells/mm³.
12. White blood cell (WBC) count <3,000 cells/mm³.
13. Clinically significant liver disease.
14. Active peptic ulcer or active bleeding from any site.
15. Bleeding from any site within the prior 8 weeks requiring active medical or surgical attention.
16. If femoral access is planned, significant peripheral arterial disease which precludes safe insertion of a 6F sheath.
17. History of bleeding diathesis or coagulopathy or will refuse blood transfusions.
18. Cerebrovascular accident or transient ischemic attack within the past 6 months, or any permanent neurologic defect attributed to CVA.
19. Known allergy to the study stent components cobalt, nickel, chromium, molybdenum, Carbosil®, PBMA, or limus drugs (ridaforolimus, zotarolimus, tacrolimus, sirolimus, everolimus, or similar drugs or any other analogue or derivative or similar compounds).
20. Known allergy to protocol-required concomitant medications such as aspirin, or DAPT (clopidogrel, prasugrel, ticagrelor), or heparin and bivalirudin, or iodinated contrast that cannot be adequately pre-medicated.
21. Any co-morbid condition that may cause non-compliance with the protocol (e.g. dementia, substance abuse, etc.) or reduced life expectancy to <24 months (e.g. cancer, severe heart failure, severe lung disease).

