22. Patient is participating in or plans to participate in any other investigational drug or device clinical trial that has not reached its primary endpoint.
23. Women who are pregnant or breastfeeding.
24. Women who intend to procreate within 12 months after the baseline procedure (women of child-bearing potential who are sexually active must agree to use a reliable method of contraception from the time of screening through 12 months after the baseline procedure).
25. Patient has received an organ transplant or is on a waiting list for an organ transplant.
26. Patient is receiving or scheduled to receive chemotherapy within 30 days before or any time after the baseline procedure.
27. Patient is receiving oral or intravenous immunosuppressive therapy or has known life-limiting immunosuppressive or autoimmune disease (e.g., HIV). Corticosteroids are allowed.

Angiographic Exclusion Criteria (visual estimate)

28. Unprotected left main lesions $\geq 30\%$, or planned left main intervention.
29. Bifurcation lesions with planned dual stent implantation.
30. Stenting of lesions due to DES restenosis.
31. Occlusive thrombus and/or a thrombus requiring thrombectomy in a target vessel
32. Another lesion in a target or non-target vessel (including all side branches) is present that requires or has a high probability of requiring PCI within 12 months after the baseline procedure.

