6.3.4 Point of Enrollment

Given the relatively low incidence of PCI to long lesion (8.4% in the ADAPT-DES trial), and the fact that the EluNIR 38 mm stent is approved and marketed in Israel, patients will be consented after PCI. Once a patient has met all general and angiographic eligibility criteria, a 38 mm long EluNIR stent been passed beyond the guiding catheter, and the patient has signed an informed consent (post-procedure), the patient will be enrolled into the trial. If the study stent is not advanced into the guiding catheter, the subject will not be consented and not be enrolled.

In order to minimize selection bias, all eligible patients (meeting I/E criteria and in whom a 38 mm long EluNIR stent was advanced beyond the guiding catheter) will be approached for participation in the study, regardless of final procedure outcome.

The sites will maintain a screening log of all 38 mm EluNIR stents advanced beyond the guiding catheter and document eligibility and patient consent versus refusal to participate in the study.

The screening and enrollment process is displayed in [Figure 1](#).

[figure not shown]

Figure 1: Screening and Enrollment Flow Chart

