6.4.3 Staged Procedures

6.4.4 Planned staged procedures are not allowed. All non-target lesions should be treated prior to target lesion treatment; as specified in section 6.4.2 Pre-Dilation of Target Lesion(s)

Pre-dilation is recommended but not required. Pre-dilation can be performed per study stent labeling and per local standards. An angioplasty balloon, cutting balloon, angiosculpt scoring balloon, or atherectomy can be utilized for pre-dilation. The pre-dilation balloon should be shorter than the planned stent(s) length to limit pre-dilation injury within the area to be stented. It is recommended that a pre-dilation catheter that is 0.5 mm smaller in diameter than the reference vessel is used.

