***Angiographic confirmation of stent thrombosis**

The presence of an intracoronary thrombus that originates in the stent or in the segments 5 mm proximal or distal to the stent and presence of at least one of the following criteria within a 48-hour time window:

- Acute onset of ischemic symptoms at rest – The incidental angiographic documentation of stent occlusion in the absence of clinical signs or symptoms is not considered a confirmed stent thrombosis (silent occlusion)
- New ischemic ECG changes that suggest acute ischemic
- Typical rise and fall in cardiac biomarkers (refer to spontaneous MI definition)

- Intracoronary thrombus is defined as a spheric, ovoid, or irregular noncalcified filling defect or lucency surrounded by contrast material on 3 sides or within a coronary stenosis seen in multiple projections, or persistence of contrast material within the lumen, or a visible embolization of intraluminal material downstream.
- Nonocclusive or occlusive thrombus
- TIMI 0 or TIMI 1 intrastent or proximal to a stent up to the most adjacent proximal side branch or main branch if originates from the side branch.

[†]Pathological confirmation of stent thrombosis

Evidence of recent thrombus within the stent determined at autopsy or via examination of tissue retrieved following thrombectomy.

STROKE

Stroke is defined as the sudden onset of vertigo, numbness, dysphasia, weakness, visual field defects, dysarthria, or other focal neurological deficits due to vascular lesions of the brain such as hemorrhage, embolism, thrombosis, or rupturing aneurysm, that persists >24 hours.

SUBINVESTIGATOR

A physician-member of a clinical study team who administers investigational products, used in the clinical trial, to a subject.

SUCCESSFUL PRE-DILATION

Pre-dilation has been successfully completed without complications if all of the following apply:

- Diameter stenosis < 50%
- TIMI Grade III flow
- Lesion length still within the requirements of the protocol
- No angiographic complications or prolonged chest pain

TARGET LESION

Lesion that has met the angiographic inclusion and exclusion criteria and that is to be treated during the baseline procedure.

TARGET LESION FAILURE (TLF)

The composite rate of cardiac death, target-vessel MI or ischemia-driven TLR

TARGET VESSEL

The entire epicardial vessel in which the treated lesion is located.

TARGET VESSEL FAILURE (TVF)

The composite rate of death, target vessel-related MI or ischemia-driven TVR

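### Section 6.3 ties enrollment of complex lesions to successful pre-dilatation or thrombectomy, which conflicts with exclusion 31 and, with consent after PCI, leaves room to select on how lesion preparation went

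*Protocol*

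**What the plan says.** Protocol Section 6.3, describing the trial population, allows complex lesions and adds in parentheses that they are "enrolled after successful pre-dilatation or aspiration thrombectomy". Section 19.1 defines successful pre-dilation by four conditions: diameter stenosis below 50%, TIMI III flow, no angiographic complications or prolonged chest pain, and "Lesion length still within the requirements of the protocol".

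Other parts of the protocol bear on the same question:

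- Exclusion 31 (synopsis and Section 6.3.2) bars "Occlusive thrombus and/or a thrombus requiring thrombectomy in a target vessel", and Section 6.3.2 opens with "All exclusion criteria must be absent for the patient to be eligible for enrollment".
- Inclusion 7 (Section 6.3.1) admits complex lesions, including those with thrombus, with no condition on how lesion preparation went.
- Inclusion 3 requires that "An attempt (whether successful or not) was made to implant a 38 mm EluNIR stent". Section 6.3.1 also notes that the criteria refer to the patient's condition before PCI.
- The pre-dilation text in Section 6.4.4 says "Pre-dilation is recommended but not required".
- Section 6.3.4 places consent after PCI. To limit selection bias, it says that all eligible patients in whom the stent passed the guiding catheter "will be approached for participation in the study, regardless of final procedure outcome".

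**The concern.** The parenthesis in 6.3 does two things that the numbered criteria do not. It names aspiration thrombectomy as a way into the trial, where exclusion 31 keeps out a target-vessel thrombus that requires it. It also attaches a success condition, with its own definition in 19.1, to a step that is otherwise optional.

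The second matters because of when enrollment happens. By the time a patient is approached, the site knows how preparation and stenting went. A site that applies the parenthesis literally could decline a patient with a poorly prepared complex lesion even though the 38 mm stent was advanced. The primary endpoint is device success without 30-day MACE, and MACE includes periprocedural MI. Poor preparation plausibly bears on both components. With one arm and a descriptive analysis, the percentage and its exact interval are the whole result, and no comparator shares the bias.

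**Working it through.** **Design figure.** The plan's only design calculation is the chance of seeing at least one device-related AE: 1 − (1 − 0.032)^50 = 0.803, matching the stated 80%. It reproduces and does not depend on this point.

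**Who may enroll, text against text.**

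| Patient (38 mm stent advanced beyond the guiding catheter) | Section 6.3 parenthesis read as a condition | Numbered criteria and 6.3.4 |
|---|---|---|
| Target-vessel thrombus requiring aspiration thrombectomy | Enrolled | Excluded (31) |
| Complex lesion, stented without pre-dilation | Not covered | Eligible (inclusion 7; pre-dilation optional) |
| Complex lesion, pre-dilation unsuccessful by 19.1 | Not enrolled | Eligible (inclusions 3 and 7; condition before PCI) |

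The first row conflicts on plain text. The only way round it is thrombectomy that was performed but not required, a distinction the protocol never makes. The other two rows conflict if the parenthesis is operative.

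**Which angiogram decides.** Section 6.4.1 uses the immediate pre-procedure angiogram and Section 13.1 the pre-intervention angiography. Section 12 refers to a final qualification before stenting, which could be read as falling after lesion preparation. That leaves a site some room to apply the filter.

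**Per-protocol set.** Protocol Section 7.6 and SAP Section 3.0 list inclusion or exclusion deviations among the major deviations. A thrombectomy subject enrolled under 6.3 breaches exclusion 31 and so leaves the set. Failed or omitted pre-dilation breaches no numbered criterion, so it moves nobody under the listed categories.

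**Lesion length.** Section 19.1 refers to a protocol length requirement. Sections 6.3 and 6.4.5 set no limit. Section 2.1.2 gives an intended purpose of lesions up to 42 mm, which Section 2.4 adopts for this investigation. These statements do not agree.

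**Possible size (assumed counts).** The documents give no expected success rate and no frequency of failed preparation. Suppose that 45 of 50 patients would succeed:

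- Nobody omitted: 45/50 = 90.0% (exact 95% CI 78.2 to 96.7).
- One failure never enrolled: 45/49 = 91.8%.
- Two failures never enrolled: 45/48 = 93.8% (82.8 to 98.7).
- Two patients omitted, one a success and one a failure: 44/48 = 91.7%.
- Two patients omitted, both successes: 43/48 = 89.6%.

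The shift is favorable only if the omitted patients fail more often than the rest. Enrollment would also continue to about 50. If two replacements follow two omitted failures, the result is 45/50, 46/50 or 47/50, that is 90.0%, 92.0% or 94.0%. If the replacements succeed at the filtered rate of 45/48 = 0.9375, the expected value is (45 + 2 × 0.9375)/50 = 93.75%. Filling the sample restores its size but does not remove the selection.

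**The case against.** The strongest reply is that 6.3 is an overview. Its closing sentence sends the reader to the general and angiographic criteria. Those lists, Section 6.3.4 and SAP Section 1.2 all state the enrollment point without any preparation test. On that reading, exclusion 31 controls thrombectomy and the parenthesis is loose wording. Optional pre-dilation is also a general rule, and a more specific remark about complex lesions need not contradict it. This is a fair reading, but nothing in 6.3 says that the parenthesis is non-operative, and 19.1 supplies a definition that would let a site apply it.

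Several stronger readings are tempting, and the documents do not support them:

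- A reader might infer that complex lesions enter *only* after successful preparation. The word is not in the text.
- A reader might see a direct contradiction of the promise in 6.3.4. That passage concerns the final procedure outcome, and lesion preparation is an intermediate step, so the tension is weaker.
- A reader might infer that poor pre-dilation moves a subject in or out of the per-protocol set. The set turns on the numbered criteria.
- A reader might say that no lesion-length figure exists. The 42 mm intended purpose does.

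The screening log in 6.3.4 is a partial safeguard. It covers every 38 mm stent advanced beyond the guiding catheter, with eligibility and consent, and SAP Section 5.1.1 tabulates numbers screened and enrolled. Omissions could therefore be counted. Their outcomes could not be recovered, because data collection starts only after consent (Section 6.1.4). The affected group is also narrow: complex, poorly prepared, with the stent still advanced.

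**Conclusion.** The point holds as an inconsistency with a possible effect on selection. The conflict between 6.3 and exclusion 31 is plain. The poor fit with optional pre-dilation, inclusion 7 and assessment on the condition before PCI is real. The link to 6.3.4 is the weakest part.

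The direction of any bias rests on two assumptions: that some sites treat the parenthesis as a condition, and that poorly prepared lesions fail more often. Its size is unknown. A reader might take the step from 90.0% to 93.8% as an estimate of bias, but it only illustrates what two omitted failures would do at this sample size. The change is worth making because it costs little and settles who enters the primary analysis.

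**What to change.** Amend Section 6.3 to say that enrollment is decided by the numbered criteria, assessed on the condition before PCI, plus passage of the 38 mm stent beyond the guiding catheter and consent. State there that success of lesion preparation is not an enrollment condition.

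Two matters are for the sponsor to reconcile, and no particular answer is proposed here:

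- the thrombectomy wording in 6.3 with exclusion 31 in the synopsis and Section 6.3.2;
- the lesion-length line in 19.1 with the absence of a limit in 6.3 and 6.4.5 and with the 42 mm intended purpose in 2.1.2 and 2.4. Deleting the 19.1 line alone would leave the last two in disagreement.

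The cost is a wording amendment. Sample size, endpoints and analyses do not change.

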6.3.1 Inclusion Criteria for Subject Selection

All inclusion criteria must be present for the patient to be eligible for enrollment.

Note: the I/E criteria refer to the patient's baseline condition prior to PCI.

General Inclusion Criteria

1. Age ≥ 18 years.
2. Patient with an indication for PCI including angina (stable or unstable), silent ischemia (in absence of symptoms a visually estimated target lesion diameter stenosis of $\geq 70\%$, a positive non-invasive stress test, or FFR ≤ 0.80 must be present), NSTEMI, or recent STEMI. For STEMI the time of presentation to the first treating hospital, whether a transfer facility or the study hospital, must be >24 hours prior to enrollment and enzyme levels (CK-MB or Troponin) demonstrating that either or both enzyme levels have peaked.
3. An attempt (whether successful or not) was made to implant a 38 mm EluNIR stent (Stent was advanced beyond the guiding catheter).

4. Non-target vessel PCI are allowed prior to enrollment depending on the time interval as follows:

a. During Baseline Procedure:

PCI of non-target vessels performed during the baseline procedure itself immediately prior to enrollment if successful and uncomplicated defined as: <50% visually estimated residual diameter stenosis, TIMI Grade 3 flow, no dissection \geq NHLBI type C, no perforation, no persistent ST segment changes, no prolonged chest pain, no TIMI major or BARC type 3 bleeding.

b. Less than 24 hours prior to Baseline Procedure:

Not allowed (see exclusion criteria #2).

c. 24 hours-30 days prior to Baseline Procedure:

- i. PCI of non-target vessels 24 hours to 30 days prior to enrollment if successful and uncomplicated as defined above.
- ii. In addition, in cases where non-target lesion PCI has occurred 24-72 hours prior to the baseline procedure, at least 2 sets of cardiac biomarkers must be drawn at least 6 and 12 hours after the non-target vessel PCI.
- iii. If cardiac biomarkers are initially elevated above the local laboratory upper limit of normal, serial measurements must demonstrate that the biomarkers are falling.

d. Over 30 days prior to Baseline Procedure:

PCI of non-target vessels performed greater than 30 days prior to procedure whether or not successful and uncomplicated.

5. Patient or legal guardian is willing and able to provide informed written consent and comply with follow-up visits and testing schedule.

Angiographic inclusion criteria (visual estimate)

6. Target lesion(s) must be located in a native coronary artery or bypass graft conduit with visually estimated diameter of ≥ 2.75 mm to ≤ 4.25 mm.
7. Complex lesions are allowed including calcified lesions (lesion preparation with scoring/cutting and rotational atherectomy are allowed), presence of thrombus, CTO, bifurcation lesions, ostial RCA lesions, tortuous lesions, bare metal stent restenotic lesions, protected left main lesions, and saphenous vein graft lesions.
8. Overlapping stents are allowed as long as the first stent implanted is the EluNIR 38 mm long stent

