Inclusion Criteria (Inclusion and Exclusion Criteria refer to patient's baseline condition prior to index PCI)	
General Inclusion Criteria:
 
1. Age \geq 18 years.2. Patient with an indication for PCI including angina (stable or unstable), silent ischemia (in absence of symptoms a visually estimated target lesion diameter stenosis of $\geq 70\%$, a positive non-invasive stress test, or FFR ≤ 0.80 must be present), NSTEMI, or recent STEMI. For STEMI the time of presentation to the first treating hospital, whether a transfer facility or the study hospital, must be >24 hours prior to enrollment and enzyme levels (CK-MB or Troponin) demonstrating that either or both enzyme levels have peaked.3. An attempt (whether successful or not) was made to implant a 38 mm EluNIR stent (Stent was advanced beyond the guiding catheter).4. Non-target vessel PCI are allowed prior to the screening for eligibility depending on the time interval and conditions as follows:
a. During Baseline Procedure: PCI of non-target vessels performed during the baseline procedure itself immediately prior to screening for eligibility, if successful and uncomplicated defined as: $<50\%$ visually estimated residual diameter stenosis, TIMI Grade 3 flow, no dissection \geq NHLBI type C, no perforation, no persistent ST segment changes, no prolonged chest pain, no TIMI major or BARC type 3 bleeding.b. Less than 24 hours prior to Baseline Procedure: Not allowed (see exclusion criteria #2).c. 24 hours-30 days prior to Baseline Procedure:
i. PCI of non-target vessels 24 hours to 30 days prior to the baseline procedure if successful and uncomplicated as defined above.ii. In addition, in cases where non-target lesion PCI has occurred 24-72 hours prior to the baseline procedure, at least 2 sets of cardiac biomarkers must have been drawn at least 6 and 12 hours after the non-target vessel PCI.

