Long-length stenting has particularly poor outcomes when bare metal stents are used.⁽⁶⁾ Moreover, treatment of a long coronary lesion with multiple stents, has been associated with serious complications such as significantly increased risk of stent thrombosis or restenosis at the gap between adjacent stents⁽⁷⁾, as the vessel is exposed to more stent's struts, polymer, and larger drug dose is delivered to the intima at the site of the stent's overlap.⁽⁸⁾ As such, implanting long DES, could potentially reduce the need to use multiple stents in long coronary lesions.

The EluNIR is a new DES which uses a closed-cell design and an improved delivery system and therefore may improve outcomes compared to other drug eluting stents. The present trial is aimed at further assessing the safety and efficacy of the long (38 mm) EluNIR stent which is approved and marketed OUS. The trial will include a diverse population representative of contemporary stent use. The trial will enroll a broad population including patients with ACS (unstable angina, NSTEMI, and STEMI) as well as complex lesions. The inclusion of patients with AMI and particularly STEMI is justified given that the majority of PCIs are in patients with ACS with STEMI accounting for up to 30% of ACS cases. In order to reduce the potential for confounding, patients with STEMI will be enrolled only after 24 hours have elapsed from their initial hospital presentation. Typically, such patients will have already undergone primary PCI of the culprit lesion. Stent thrombosis is increased in the setting of primary PCI mostly in the first 24 hours.⁽⁹⁾ Therefore, confounding is unlikely and furthermore subjects will be stratified in the trial by ACS vs. non-ACS status.

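### The STEMI 24-hour window is counted to enrollment, which follows PCI, and so conflicts with the note that eligibility is judged on the patient's state before PCI

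*Protocol*

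**What the plan says.** **Where the clock ends.** Protocol 6.3.1, inclusion 2, requires that the STEMI presentation time "must be >24 hours prior to enrollment". The synopsis version reads "must be >24 hours prior to enrollment and enzyme levels (CK-MB or Troponin) demonstrating that either or both enzyme levels have peaked". Protocol 6.3 describes the population as "STEMI >24 hours prior to enrollment and stable".

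**When enrollment happens.** Protocol 6.3.4 states that "patients will be consented after PCI". Once the eligibility criteria are met, the stent has passed the guiding catheter and "the patient has signed an informed consent (post-procedure), the patient will be enrolled into the trial". SAP 1.2 repeats this. Section 6.3.4 sets no maximum interval between PCI and consent.

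**What points the other way.** A note in the synopsis, repeated at the start of 6.3.1, says the criteria describe the patient before PCI. Exclusion 1 (6.3.2) bars STEMI within 24 hours of presentation or with enzymes not yet peaked, but does not say at what moment the 24 hours are assessed.

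**Purpose.** Protocol 3.1 says "patients with STEMI will be enrolled only after 24 hours have elapsed from their initial hospital presentation", in order to limit confounding. It adds that early stent thrombosis after primary PCI falls mostly in the first 24 hours, and that such patients will typically have had their primary PCI already.

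**The concern.** A time rule needs a start and an end. The start, presentation to the first treating hospital, is clear. The end is an event that in this trial comes after the treatment under study. An enrollment end point serves its purpose when enrollment precedes the procedure. With consent after PCI, it lets post-procedure hours count toward a waiting period that section 3.1 justifies by what happens around primary PCI.

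At stake is whether the rule is applied uniformly. If one site follows the clock in inclusion 2 and another follows the note, the same early STEMI patient is enrolled at the first and not at the second. Under Protocol 6.1.6, a patient who consented but was judged ineligible and is not in the full analysis set (FAS) belongs only to the safety set. If the patient has been enrolled, Protocol 7.6 and SAP 3.0 make an eligibility deviation a ground for removal from the per-protocol set. Membership of the FAS and the per-protocol set can therefore turn on which sentence is followed.

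**Working it through.** **1. The plan's own figure.** No stated figure depends on this clock. The sample-size statement (Protocol 7.1) reproduces: 1 − (1 − 0.032)^50 = 0.803, against the stated 80%. It is unaffected.

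**2. The two readings.** Let d be the hours from presentation to the index PCI and c the hours from PCI to signed consent. Neither is given in the documents; the values below are assumptions.

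- Literal inclusion 2: the time clause is met if d + c > 24.
- Pre-PCI reading (the note): the time clause is met only if d > 24.

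Cells show d + c and whether the literal clause is met.

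| d (h) | c = 2 | c = 12 | c = 18 | c = 24 | Pre-PCI reading |
|---|---|---|---|---|---|
| 1 | 3, no | 13, no | 19, no | 25, yes | no |
| 2 | 4, no | 14, no | 20, no | 26, yes | no |
| 6 | 8, no | 18, no | 24, no | 30, yes | no |
| 12 | 14, no | 24, no | 30, yes | 36, yes | no |
| 23 | 25, yes | 35, yes | 41, yes | 47, yes | no |

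With consent a day after PCI, every row passes the literal clause and none passes the pre-PCI reading.

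**3. Does another provision settle it?**

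- *Exclusion 1.* Read with the note, it bars every row (d < 24). Read alone, it has no end point and cannot decide between the readings.
- *Exclusion 2.* It bars PCI in the 24 hours before the baseline procedure. It does not apply when the primary PCI is itself the baseline procedure.
- *Enzyme clause.* Under the note, the peak must precede PCI, and Table 1 footnote 3 attaches the peak to the pre-procedure sample. Protocol 6.1.4.2, however, allows missing baseline biomarkers to be drawn after enrollment.
- *The note.* It cannot govern every criterion. Inclusion 3 (stent already advanced) and inclusion 5 (consent) are not purely pre-PCI conditions, and 6.1.4.3 has general eligibility screened after the stent attempt.

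**4. The same end point elsewhere.** Item 4c(i) of 6.3.1 reads "PCI of non-target vessels 24 hours to 30 days prior to enrollment if successful and uncomplicated as defined above". Its own heading, the synopsis version and Table 3 count to the baseline procedure. The lower limit is closed anyway by item 4b, exclusion 2 and Table 3, so only a narrow ambiguity at the 30-day edge remains.

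**5. Scale.** If 50 subjects are evaluable, any one subject is 1/50 = 2 percentage points of the primary endpoint. For example, 49/50 has an exact 95% interval of 89.4% to 99.9%, and 48/50 has 86.3% to 99.5%. This is the weight of any single subject, not an estimate of the effect of this wording.

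**The case against.** The strongest reply is that the document as a whole favors the pre-PCI reading. The note covers inclusion and exclusion criteria alike, and every exclusion must be absent, so a patient stented two hours after presentation fails exclusion 1 whenever consent is signed. The synopsis population statement, Protocol 6.1.1 and 7.1, and SAP 1.2 attach the 24 hours to the indication for PCI and do not mention enrollment. Protocol 13.1 confirms final eligibility on the pre-intervention angiogram, and 13.2 expects no emergency treatment. Exclusion 31 removes target vessels with occlusive thrombus or thrombus needing thrombectomy. The study is also descriptive, with no hypothesis test or performance threshold.

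Much of this stands. A reader might infer that a next-day signature makes primary-PCI STEMI patients eligible. The documents do not support that: meeting the time clause is not enough, because the note, exclusion 1 and the enzyme clause all count against such a patient.

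What does not stand is that nothing needs correcting. The statements tied to the indication also name no end point. The only STEMI-specific sentences that do name one, in inclusion 2 and section 6.3 (and, in effect, section 3.1), name enrollment. A site could reasonably prefer a specific clock to a general note that demonstrably does not fit every criterion. Exclusion 31 does not settle the matter either: section 6.3 foresees enrolling complex lesions after aspiration thrombectomy.

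**Conclusion.** The point holds as an internal contradiction in a stated eligibility rule. Inclusion 2 and section 6.3 count to an event after PCI, the note places the assessment before PCI, and exclusion 1 leaves its end point open. The contradiction runs against the purpose given in section 3.1 and can change who is in the FAS and the per-protocol set. It should be corrected, but it does not of itself undermine the trial.

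The number of patients affected cannot be computed. It depends on how many STEMI patients are stented within 24 hours of presentation and how long after PCI they consent, and the documents give neither. Figure 1, the enrollment flow chart, was not available for this check.

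A reader might also infer that the wording biases 30-day MACE by selecting patients who survive to consent. That does not follow from this clock. Surviving to sign is required of every subject under post-PCI consent, STEMI or not, and changing the end point would not remove it.

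**What to change.** Reconcile the passages to one end point that agrees with the note:

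- In inclusion 2 (synopsis and 6.3.1) and in section 6.3, count the STEMI window to the baseline procedure instead of to enrollment.
- In exclusion 1 (synopsis and 6.3.2), state the same end point.
- As a minor consistency edit, make item 4c(i) of 6.3.1 match its own heading, the synopsis and Table 3.

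The baseline procedure is already the reference point in exclusion 2, Table 3 and synopsis item 4c(i), so nothing new is introduced. The cost is a wording amendment. STEMI patients whose index PCI falls within 24 hours of presentation, probably few, become clearly ineligible. No analysis, sample size or endpoint definition changes.
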